##### 3.1.2. MAD

Screened: All subjects with an informed consent date will be part of this population.

Randomized: All subjects with a randomization date.

Safety Population: the population for safety analysis will consist of all subjects who receive any QR-010 or placebo.

Subjects will be analysed according to the actual treatment received (this is checked versus kit numbers, which may be different to randomization received).

Exploratory Analysis Population: the population for efficacy (clinical activity) analysis will consist of all subjects randomized who receive at least one dose of QR-010 or placebo.

Subjects will be analysed according to the actual treatment received. Applying this criterion is consistent with the objective of exploratory of clinical efficacy in this relatively small sample size phase 1 safety and tolerability study.

Pharmacokinetics (PK) Population: the population for PK analyses will consist of all subjects who receive at least one dose of QR-010 and who have sufficient drug concentrations to support analysis. For subjects in whom dosing was discontinued early, pharmacokinetic parameters for week 4, dose 12 will not be generated, but all available PK concentrations in serum, urine and sputum will be listed regardless of time of last dose; however PK parameters will be generated on all other days where study dose was administered as per protocol.

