The AEs of Interest listed in Table 2 are AEs commonly seen with inhaled products. If AEs of interest occur at a Grade 2 level or higher in a single subject in a cohort, then an additional 4 subjects will be added to the cohort. Any of the Grade ≥ 2 toxicities shown in Table 2, as well as

any other respiratory AEs reported, will be evaluated and considered when making dose escalation decisions. If no additional subjects experience any Grade ≥ 2 AEs of Interest, dose escalation may proceed (if recommended by the DSMC).

The Investigator will base decisions to de-escalate to a lower dose, hold the dose (delay or skip), or discontinue study drug for an individual subject using the CTCAE (modified for CF) toxicity grades, in consultation and agreement with the Sponsor’s Medical Monitor. In addition to the CTCAE (modified for CF) toxicity grades, the Investigator should also review the stopping rules in Section 5.5.3 with regard to decreases in FEV₁.

For the multiple dose cohorts, subjects who experience a DLT (defined in Section 4.4) should be discontinued from study drug (whether or not the event resolves), and the End of Treatment Visit procedures should be conducted. An End of Study Visit should also be conducted 28 days after the last study drug dose.

Table 2: Adverse Events of Interest

| Adverse Event of Interest | Symptoms (Grade ≥ 2 per CTCAE or as Specified Below) |
|--------------------------------------|------------------------------------------------------------------------------------------------------------------------------------------|
| Atelectasis | Symptomatic (eg, dyspnea, cough); medical intervention indicated (eg, chest physiotherapy, suctioning); bronchoscopic suctioning |
| Hypotension | non-urgent medical intervention indicated |
| Bronchospasm | symptomatic, medical intervention indicated |
| Liver Function Test Elevation | alanine aminotransferase (ALT) > 3-5 x ULN or aspartate aminotransferase (AST) > 3-5 x ULN AND a doubling from the baseline value |
| Pneumonitis | Symptomatic; medical intervention indicated; limiting instrumental ADL |
| Crackles | Scattered or focal |
| Dyspnoea | Shortness of breath with minimal exertion; limiting instrumental ADL |
| Hypoxia | Decreased oxygen saturation with exercise (eg, pulse oximeter < 88%); intermittent supplemental oxygen |

ADL = Activities of Daily Living

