7.1 Visit and Assessment Windows

The flexibility regarding scheduling of study days and corresponding procedures differ depending on the cohort and phase of the study. The timing of assessments, procedures and sample collections outlined in the protocol are nominal times. It is understood that in the phase 1 setting, actual times will approximate rather than match the nominal times exactly. Actual times are to be recorded in the source documentation and in the case report forms (CRFs), and, if any time points are missed, the reasons are also recorded.

For the SAD cohorts, there is no flexibility regarding the timing of the scheduled study days in relation to dose Day 1.

For the MAD cohorts, there is some flexibility regarding the timing of the scheduled study days in relation to dose Day 1. The description of procedures assumes a Monday-Wednesday-Friday dosing schedule. An alternative dosing schedule can be used, provided that there is at a minimum 2 days between doses, and a maximum of 4 days between doses. Missed doses are to be recorded as such, and the overall treatment period should remain at 4 weeks, and not be extended to accommodate the missed doses. Missed doses are to be recorded in the CRF.

Details regarding acceptable windows for timing of study procedures for both the SAD and MAD cohorts can be found in the Laboratory Manual.

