##### Definition of target dose visits dates for MAD:

When possible, visits windows are defined with the doses dates.

- If a subject receives all 12 doses: target dates/times are the doses dates/times
- If a subject receives less than 12 doses: use the table below for definition of expected dates.
  - If there is a dose in the window EXPDATE +/-1 days then target visit date=this particular dose date.
  - If there is no dose in the window EXPDATE +/-1 days then the subject has missed the dose at the visit or missed the visit,
  - Then EXPDATE will be taken as the target visit date, with time 00:00.

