**Table 26: Planned Pharmacokinetic Parameters by Matrix and Study Day**

Parameter	Definition	Calculation
SAD, Study Day 1, Serum PK Parameters		
C max	Maximum serum concentration	Observed
T max	Time of maximum serum concentration	Observed
AUC last	Area under the concentration-time curve from 0 to the last quantifiable serum concentration	Linear-Log trapezoidal method
AUC inf	Area under the concentration-time curve from 0 extrapolated to infinite	Calculated as AUC 0-last + C est,last /λ z , where C est,last is the estimated last measurable concentration
T 1/2	Apparent terminal elimination half-life	ln(2)/λ z , where λ z is the apparent first-order terminal elimination rate constant.
λ z	Terminal elimination rate constant	Log-linear regression of the concentration-time curve during terminal elimination
Cl/F	Apparent Clearance	Dose/AUC inf
V d /F	Apparent volume of distribution	Dose/AUC inf * λ z
SAD, Study Day 1, Urine PK Parameters		
A e	Amount excreted unchanged in the urine	Cumulative: Sum of concentration* volume per collection interval
Fe%	Fraction of Dose excreted	Calculated as A e /Dose, where A e is the amount of unchanged drug excreted in urine during a collection

	unchanged in the urine	interval and D is the Dose
Clr	Renal Clearance	Calculated as $Ae_{24}/AUC_{24}$ where Ae is the amount of unchanged drug excreted in urine during the first 24 hours post-dose and $AUC_{24}$ is the Area under the concentration versus time curve from 0 to 24 hr.
MAD, Week 1, Dose 1, Serum		
Cmax	Maximum serum concentration	Observed
Tmax	Time of maximum serum concentration	Observed
AUCtau	Area under the concentration-time curve from 0 to the end of the dosing interval (tau, where tau will equal 48 hours).	Linear-log trapezoid
MAD, Week 4, Dose 12, Serum		
Ctrough	Trough serum concentration	Observed
Cmax	Maximum serum concentration	Observed
Tmax	Time of maximum serum concentration	Observed
AUCtau *	Area under the concentration-time curve from 0 to the end of the dosing interval (tau, where tau will equal 48 hours).	Linear-log trapezoid
Css	Steady-state concentration	$AUC_{tau}/tau$ , where tau will equal 48 hours

Ro	Accumulation ratio	AUCtau (week 4, dose 12)/ AUCtau (week 1, dose 1)
Ro,Cmax	Cmax, accumulation ratio	Cmax(week 4, dose 12)/ Cmax (week 1, dose 1)

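### The SAP withholds dose-12 PK parameters only after early discontinuation, so subjects who skipped dose 10 or 11, or had dose 12 well over 48 h after dose 11, are summarised as if dosed every 48 h

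*SAP*

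**What the plan says.** SAP 3.1.2 defines the MAD PK population as "all subjects who receive at least one dose of QR-010 and who have sufficient drug concentrations to support analysis". It sets no minimum number of doses. On dose 12 it adds: "For subjects in whom dosing was discontinued early, pharmacokinetic parameters for week 4, dose 12 will not be generated". The same sentence goes on to say that "PK parameters will be generated on all other days where study dose was administered as per protocol"; that condition is attached to days other than dose 12.

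The protocol expects incomplete dosing. Section 7.1 states "Missed doses are to be recorded as such, and the overall treatment period should remain at 4 weeks", and treatment is not extended to make up the loss. It also permits a calendar other than Monday-Wednesday-Friday, "provided that there is at a minimum 2 days between doses, and a maximum of 4 days between doses". Section 4.3 lets the investigator "hold the dose (delay or skip") for an individual subject. The SAP's own visit-date rules (4.2.7.1) have a branch for subjects with fewer than 12 doses, for whom an expected date with no dose nearby means "then the subject has missed the dose at the visit or missed the visit".

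SAP Table 26 fixes tau at 48 h for dose 12. It derives Ctrough, Cmax, Tmax, AUCtau, Css, CL/F and V/F there, and defines Ro as "AUCtau (week 4, dose 12)/ AUCtau (week 1, dose 1").

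**The concern.** The SAP already accepts that dosing history decides whether dose-12 parameters are valid, but applies this to one case only. A subject who skips dose 11 and is dosed on Day 26 has not discontinued, so the rule as written keeps that subject in. The trough then follows a 96 h gap, and Ro compares an under-loaded interval with the first dose.

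Accumulation over repeated doses is what the MAD part adds to the single-dose PK, and Protocol 13.8 judges steady state from troughs. A skipped dose cannot raise trough or Ro under linear kinetics, so the error runs towards less apparent accumulation and higher apparent clearance. Table 26 also reports an Accumulation Index computed from the elimination rate and tau alone, which does not depend on which doses were given. Beside an affected subject's observed Ro, it would make a missed dose look like a failure to accumulate.

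**Working it through.** **Inputs.** Scheduled dose times, from the schedules of assessments: 0, 48, 96, 168, 216, 264, 336, 384, 432, 504, 552 and 600 h. Tau = 48 h (Table 26). Six QR-010 subjects per cohort (SAP 4.1). The documents give no half-life, so it is assumed and varied.

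**The plan's own figure.** Dose 12 minus dose 11 = 600 − 552 = 48 h, which agrees with tau.

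**What a skip does to the gaps.** Without dose 11, the gap before dose 12 is 600 − 504 = 96 h, or 4 days, which is inside the protocol's limit. Without dose 10, the gap from dose 9 to dose 11 is 552 − 432 = 120 h, or 5 days, which is outside it; the interval before dose 12 stays at 48 h but carry-over is lost.

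**Model.** One compartment, instantaneous input, linear superposition, with k = ln 2 / half-life and T the time of dose 12:

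- Trough before dose 12, relative to the first-dose peak: sum of exp(−k(T − t_i)) over the earlier doses given.
- Ro = 1 + that sum.
- CL/F is proportional to 1/Ro.

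**Worked case, half-life 48 h.** On the full schedule the sum is 0.920, of which dose 11 contributes 0.500 and dose 10 contributes 0.250.

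- Full schedule: Ro = 1.92.
- Dose 11 skipped: sum 0.420, Ro = 1.42. Ro changes by −26% and trough by −54%. CL/F rises by 1.92/1.42 − 1 = 35%.
- Dose 10 skipped: sum 0.670, Ro = 1.67, a change of −13%.
- All 12 doses given, but dose 12 at T = 648 h (Day 28, 96 h after dose 11): sum 0.460, Ro = 1.46.
- Accumulation Index: 1/(1 − 0.5) = 2.00 in every case.

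**Other half-lives.** The cohort columns assume one dose-11 skipper among six otherwise identical subjects.

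| Half-life (h) | Ro, full | Ro, dose 11 skipped | Trough change | Ro, dose 10 skipped | Ro, dose 12 at 96 h | Cohort mean Ro | Cohort mean trough |
|---|---|---|---|---|---|---|---|
| 12 | 1.07 | 1.00 (−6%) | −94% | 1.06 (−0.4%) | 1.00 | −1.0% | −15.7% |
| 24 | 1.32 | 1.07 (−19%) | −77% | 1.26 (−5%) | 1.08 | −3.1% | −12.9% |
| 48 | 1.92 | 1.42 (−26%) | −54% | 1.67 (−13%) | 1.46 | −4.3% | −9.1% |
| 96 | 3.12 | 2.41 (−23%) | −33% | 2.62 (−16%) | 2.50 | −3.8% | −5.6% |

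Over half-lives from 8 to 336 h, the fall in cohort mean Ro runs from 0.3% to 4.3% and in mean trough from 2.5% to 16%. Missing both doses 10 and 11 lowers the subject's Ro by 24%, 39% and 39% at 24, 48 and 96 h. First-order absorption (rate 0.5/h, assumed) gives nearly the same percentages.

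**Spread.** At 48 h, five values of 1.92 and one of 1.42 give a mean of (5 × 1.92 + 1.42)/6 = 1.84. The SD is 0.50/√6 = 0.20, so the CV is about 11%, produced by the skip alone; the skipper is also the minimum.

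**The case against.** The strongest objection is that little follows from the gap. Half-life and number of skippers are both unknown. At 12 h or less Ro barely moves and the trough is already near zero. A cohort mean Ro that falls by 4% at worst is modest, and the SAP also reports the median. All of this stands and limits the size of the point.

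A reader might infer that understated accumulation could let dosing escalate unsafely. The documents do not support that: Protocol 4.3, 4.5 and 12.1 base escalation and the MTD on DLTs, adverse events and DSMC safety review, not on Ro or dose-12 trough.

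The affected group may also be small. Doses are given and observed in clinic. Drug-related SAEs, drug-related Grade 2 or higher events and large FEV1 falls lead to permanent discontinuation (Protocol 5.5.3.2), which the SAP rule already covers. Skips would not be hidden either: missed doses go in the CRF, exposure is summarised by dose visit, and individual PK results are listed. But listing a skip does not remove it from the summary.

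The as-per-protocol wording in SAP 3.1.2 might be stretched to cover dose 12. It is attached to other days, and a skipped dose 11 leaves a gap that the protocol permits. The non-evaluable rule in SAP 4.9 concerns missing concentration data and is discretionary. Deviation grading (SAP 3.2) removes nobody. The post hoc population of at least 10 of 12 doses is for efficacy and would admit these subjects.

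One tempting argument should be dropped. SAP Table 5 pairs dose 12 with Day 26, but it belongs to the visit windows. There is no PK window table, so it does not show how the PK analysis numbers doses.

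**Conclusion.** The gap is real on the text. Followed exactly, the SAP puts subjects with a skipped dose 10 or 11, or a clearly prolonged interval before dose 12, into dose-12 summaries computed as if they were on a 48 h schedule. The direction is downward for trough and Ro and upward for CL/F, given linear kinetics and carry-over.

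For the individual the effect can be substantial: up to about a quarter of Ro for a skipped dose 11, and less for dose 10 alone. For a cohort with one dose-11 skipper it is small for mean Ro and moderate for mean trough, with a visible effect on minimum and CV. The percentages rest on an assumed half-life, and the documents do not establish that any subject skipped. The point concerns the accuracy of a descriptive secondary PK result and is worth correcting; it is not a safety defect in the escalation scheme.

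**What to change.** In SAP 3.1.2, replace the early-discontinuation condition with wording such as: Dose-12 parameters (Ctrough, Cmax, AUCtau, Css, Ro, Ro,Cmax, CL/F, V/F) are summarised only for subjects who received doses 10, 11 and 12 in full and whose actual dosing times give about 48 h between doses 11 and 12, within a tolerance fixed before database lock. For all other subjects, concentrations and any parameters are listed and flagged with the doses missed and the actual interval. The all-subject summary may be shown as a sensitivity display.

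The tolerance must not be the protocol's 2-to-4-day allowance. That would admit a 96 h gap, which at a 48 h half-life gives Ro 1.46, almost the same as the 1.42 of the dose-11 skipper being excluded. This is an analysis rule only and changes no dosing instruction.

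The cost is one SAP paragraph and a smaller n. With six active subjects per cohort, several missed or delayed doses could leave fewer than the three evaluable subjects that SAP 4.9 requires for summary statistics. Subjects on a permitted alternative calendar with a longer last interval would also move to the listings. Earlier skips are not screened: at a 96 h half-life, missing dose 9 lowers Ro from 3.12 to 2.82. The flag should therefore show every missed dose.

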### **3.2. Protocol Deviations**

Protocol deviations are defined as a deviation from the approved protocol.

Prior to database lock, ProQR's Medical Monitor will review the study's protocol deviation list and will define/document which subjects/deviations are considered minor/major protocol deviations.

Protocol deviations will be summarized by characteristics (Minor/Major), category and reason. All protocol deviations will be presented in data listings.

## **4. STATISTICAL METHODS**

### **4.1. Sample Size Justification**

This is a Phase 1 safety study designed to evaluate the safety, tolerability and PK of QR-010. The sample size is not based on power calculations. It is chosen based on clinical experience and considered to be adequate to fulfill the objectives of the study.

Approximately 64 subjects will be enrolled in the study, with 8 subjects per cohort (6 QR-010 and 2 placebo), 32 each in the SAD and MAD portions of the study. The exact number of subjects enrolled is dependent on whether any dose levels are to be expanded due to the occurrence of AEs of interest.

### **4.2. General Statistical Methods and Data Handling**

#### **4.2.1. Baseline Values**

Unless otherwise specified, baseline data is defined as the data most recently collected prior to the first dose.

For Sweat Chloride, baseline is the average of all assessments of the day the closest to first dose, first dose day after dose time excluded.

#### **4.2.2. Change (absolute) and % Change (relative change)**

Change and % change (relative) from baseline is calculated as:

Change = Post baseline visit value – baseline value.

% Change =  $100 * ((\text{Post baseline visit value} - \text{baseline value}) / \text{baseline value})$ .

If either the baseline or visit value is missing, the change from baseline/% change is set to “missing”.

#### **4.2.3. Study Day**

Study Day is the number of days since the administration of the first dose of study drug, which is counted as Study Day 1. If the assessment date is after the date of the first dose, the study day is calculated as (date of assessment - date of the first dose administration + 1). If the assessment date is prior to the date of the first dose, the study day is calculated as (date of assessment - date of the first dose administration). All assessments prior to Study Day 1, including the Screening and Check-In visits, will have negative study days.

#### **4.2.4. End of Study Date**

End of study date is defined as the date when a subject completes the study (all doses given and all visits completed) or withdraws from the study early, it is computed as the maximum date for a subject-visit taken from any database panel.

#### **4.2.5. Table Shell**

Separate outputs will be produced for the SAD cohorts and the MAD cohorts. In general, the total group will be presented for disposition, baseline information, and treatment exposure, unless otherwise specified.

**Table 3: Header for the SAD Cohort**

	Placebo	QR-010 6.25 mg	QR-010 12.5 mg	QR-010 25 mg	QR-010 50 mg	Total SAD (optional)
Screened	...	...	...	...	...	...
Screen failure						
Treated						
Exploratory Analysis Population						
Safety Population						
Xxx						

**Table 4: Header for the MAD Cohort**

	Placebo	QR-010 6.25 mg	QR-010 12.5 mg	QR-010 25 mg	QR-010 50 mg	Total MAD (optional)
Screened	...	...	...	...	...	...
Screen failure						
Treated						
Exploratory Analysis Population						
Safety Population						
xxx						

#### 4.2.6. Multiple Comparisons/Multiplicity

Due to the exploratory nature of the study, all tests for exploratory efficacy are conducted at alpha level 5%, two-sided (or 2.5% one-sided), and there will be no adjustment for multiplicity.

#### 4.2.7. Visit Windows

##### 4.2.7.1. General Rules

##### Definition of target visit dates for SAD:

Day 1 is defined as the date of first (and unique) dose. Day 2,3,4,8 are defined relatively to Day 1 (Ex: Day 4=Day 1+3).

##### Definition of target dose visits dates for MAD:

When possible, visits windows are defined with the doses dates.

- If a subject receives all 12 doses: target dates/times are the doses dates/times
- If a subject receives less than 12 doses: use the table below for definition of expected dates.
  - If there is a dose in the window EXPDATE +/-1 days then target visit date=this particular dose date.
  - If there is no dose in the window EXPDATE +/-1 days then the subject has missed the dose at the visit or missed the visit,
  - Then EXPDATE will be taken as the target visit date, with time 00:00.

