7.4.12 Follow-up Visits—7 and 28 Days After Last Dose

Follow-up visits will occur 7 and 28 days after the last dose of study drug (dose 12).

If at any time during the study the subject discontinues the study early, the subject should return to the clinic to complete the End of Treatment Visit procedures below, and should also return to the clinic to complete the End of Study Visit procedures 28 days after the last study drug dose.

7.4.12.1 7 Days After Last Dose—End of Treatment Visit

1. Subject self-completes the CFQ-R prior to all other procedures and assessments
2. Complete physical examination (including body weight)
3. Vital signs
4. Oximetry
5. Concomitant medication review
6. AE review
7. Chest Xray
8. 12-lead ECG
9. Spirometry
10. Obtain blood and urine samples for local laboratory assessments
11. Obtain urine or blood for pregnancy test (for women of child-bearing potential)
12. Obtain blood samples for PK
13. Obtain sputum sample for the following local laboratory assessment:
 - Microbiology organism identification
14. Obtain blood and sputum samples for inflammatory biomarkers
15. Obtain sample for sweat chloride determination

7.4.12.2 28 Days After Last Dose—End of Study Visit

1. Subject self-completes the CFQ-R prior to all other procedures and assessments
2. Complete physical examination (including body weight)
3. Vital signs
4. Oximetry
5. Concomitant medication review
6. AE review
7. Spirometry
8. Obtain blood and urine samples for local laboratory assessments
9. Obtain urine or blood for pregnancy test (for women of child-bearing potential)
10. Obtain blood and sputum samples for inflammatory biomarkers

11. Obtain serum samples for PK
12. Obtain sample for sweat chloride determination

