**Table 5: Target Visit/Days for MAD**

Dose (Visit)	Expected date EXPDATE (Dose n-1 date + expected number of days)	Target Dose Visit Date
Dose 1 (Day 1)	Day 1	Dose 1 date
Dose 2 (Day 3)	Dose 1 date + 2 days (i.e. 3-1), time 00:00	
 
• If any dose within expected date +/-1 days then = this dose date,
 
• else = expected date (i.e. = Dose 1 date + 2 days)
 

Day 4	Day 3 Target date+1 day	Day 3 Target date+1 day
Dose 3 (Day 5)	Day 3 Target date + 2 days (5-3), time 00:00	
 
• If any dose within expected date +/-1 days then = this dose date,
 
• else = expected date (i.e. Day 3 Target Date + 2 days)
 

Dose 4 (Day 8)	Day 5 Target date + 3 days (8-5), time 00:00	"
Dose 5 (Day 10)	Day 8 Target date + 2 days, time 00:00	"
Dose 6 (Day 12)	Day 10 Target date + 2 days, time 00:00	"
Dose 7 (Day 15)	Day 12 Target date + 3 days, time 00:00	"
Dose 8 (Day 17)	Day 15 Target date + 2 days, time 00:00	"
Dose 9 (Day 19)	Day 17 Target date + 2 days, time 00:00	"
Dose 10 (Day 22)	Day 19 Target date + 3 days, time 00:00	"
Dose 11 (Day 24)	Day 22 Target date + 2 days, time 00:00	"
Dose 12 (Day 26)	Day 24 Target date + 2 days, time 00:00	"
Day 33	Day 26 Target date + 7 days	Day 26 Target date + 7
Day 54	Day 26 Target date + 28 days	Day 26 Target date + 28

For time points with time precision relative to dose (i.e. "Dose time+ XX min"), the time is computed with respect to the end time of dosing (end of inhalation).

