Day 33	Day 33	[Day 26+4 ; Day 33+7]
Day 54	Day 54	[Day 33+8 ; End of Study]

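### SAP windows for MAD subjects with fewer than 12 doses follow a notional dosing calendar, so early stoppers' 28-day visit can be tabulated as Day 33 and undosed visits can fall into post-dose rows

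*SAP*

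**What the plan says.** SAP 4.2.7.1 has two branches for MAD. A subject with all 12 doses is windowed on the actual dose dates. Otherwise the rule is: "If a subject receives less than 12 doses: use the table below for definition of expected dates". Table 5 steps from one target date to the next. If no dose lies within one day of the expected date, "EXPDATE will be taken as the target visit date, with time 00:00". The chain runs on to Day 26 whether or not dosing has stopped. Day 33 is then "Day 26 Target date + 7 days" and Day 54 is "Day 26 Target date + 28 days". A note under Table 5 says that post-dose times are counted from the end of inhalation.

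Protocol 7.4.12 requires a subject who stops early to complete the End of Treatment procedures and also to "complete the End of Study Visit procedures 28 days after the last study drug dose". Protocol 4.3 and 5.5.2 time End of Study in the same way. For End of Treatment after an early stop, the protocol gives no day beyond the visit heading, "7 Days After Last Dose—End of Treatment Visit". SAP 2.1 also describes the two visits as 7 and 28 days after last dose.

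The only special handling of early stoppers that I found in the SAP concerns PK parameters (3.1.2).

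**The concern.** Two clocks are in use. The protocol counts End of Study from the last dose given, and the SAP counts it from a dose 12 that was never given. For an early stop, the 28-day visit can therefore land in the row meant for the 7-day visit, leaving the subject's Day 54 cell empty. Separately, many windows for spirometry, laboratory tests and vital signs are bounded by a dose start or end time. At an undosed visit the SAP supplies only the 00:00 target. If that serves as the dose time, anything measured during clinic hours comes after the dose.

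Change from baseline to end of treatment in laboratory parameters, vital signs and spirometry is a secondary safety endpoint (protocol 4.1.2). Protocol Table A.1-6 identifies Day 33 as that time point. Protocol 5.5.3.2 permanently stops MAD subjects for a related Grade 2 or higher AE or an FEV1 fall of 15% or more, so the misplaced subjects may be ones of safety interest. Protocol 7.1 also foresees missed doses within an otherwise continuing course, and these take the same 00:00 rule.

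**Working it through.** **Inputs.** Table 5 steps between doses: 2, 2, 3, 2, 2, 3, 2, 2, 3, 2, 2 days. Windows: SAP Tables 7 (spirometry), 9 (hematology and chemistry) and 20 (vital signs). End of Study = last dose + 28 days (protocol 7.4.12).

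**The plan's own calendar.** Starting at Day 1, the steps give doses on Days 1, 3, 5, 8, 10, 12, 15, 17, 19, 22, 24 and 26. Then 26 + 7 = 33 and 26 + 28 = 54. This reproduces Table 5, and a completer is placed correctly.

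**End of Study after an early stop.** The Day 33 window for spirometry is "Day 26+4 ; Day 33+7", that is Days 30 to 40; vital signs have the same limits. The laboratory window opens just after Day 26, so it covers Days 27 to 40.

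| Last dose given | Its day | End of Study (+28) | Laboratory row | Spirometry and vital signs row |
|---|---|---|---|---|
| 1 | 1 | 29 | Day 33 | Day 26 post-dose |
| 2 | 3 | 31 | Day 33 | Day 33 |
| 3 | 5 | 33 | Day 33 | Day 33 |
| 4 | 8 | 36 | Day 33 | Day 33 |
| 5 | 10 | 38 | Day 33 | Day 33 |
| 6 | 12 | 40 | Day 33 | Day 33 |
| 7 | 15 | 43 | Day 54 | Day 54 |
| 8 | 17 | 45 | Day 54 | Day 54 |
| 9 | 19 | 47 | Day 54 | Day 54 |
| 10 | 22 | 50 | Day 54 | Day 54 |
| 11 | 24 | 52 | Day 54 | Day 54 |

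The laboratory error covers 6 of 11 stopping points; spirometry and vital signs have 5 of 11 in Day 33. After dose 1 only, Day 29 falls in the last Day 26 post-dose window, which stays open to Day 26 + 3 days. CFQ-R (Table 22) behaves like laboratory. Weight and sweat chloride (Tables 21 and 17) behave like spirometry, except that after dose 1 the row is plain Day 26.

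**Undosed visits and post-dose rows.** Two assumptions: 00:00 stands in for the dose start and end times, and End of Treatment is at last dose + 7 days.

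*Example, stop after dose 4:* 8 + 7 = Day 15, the notional dose 7 day. For a 10:00 visit:
- Spirometry: the last Day 15 window opens at 00:00 + 40 min = 00:40 and runs to Day 17, so the row is Day 15 60 min Post-dose.
- Laboratory: it opens at 00:00 + 90 min = 01:30 and runs to Day 17, so the row is Day 15 2h Post-dose.
- Vital signs: it opens at 01:30 and runs up to Day 16, so the row is Day 15 2h Post-dose.

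No drug was given that day.

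*All 11 stopping points* (visit at 09:00; the post-dose counts are the same at 07:00, 12:00 and 17:00):

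| End of Treatment tabulated as | Spirometry | Laboratory | Vital signs |
|---|---|---|---|
| Post-dose, dose not given | 8 | 7 | 5 |
| Pre-dose, dose not given | 2 | 2 | 5 |
| Day 33 | 1 | 2 | 1 |

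With End of Treatment at +3, +5 or +9 days instead, the post-dose counts out of 11 are 5, 9 and 5 (spirometry), 4, 6 and 4 (laboratory), and 4, 5 and 2 (vital signs).

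**Weight of one subject.** Six active subjects are planned per cohort, so one misplaced subject is 1/6, about 17%, of a full cell.

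**After re-anchoring.** With the 7-day and 28-day rows set from the actual last dose, and dose-relative rows filled only where a dose was given, 0 of 11 stopping points are misplaced. Completers are unchanged.

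**The case against.** The strongest reply has four parts.

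*The SAP never calls 00:00 a dose time.* It assigns 00:00 to the target visit date and counts post-dose times from the end of inhalation. With no inhalation, the windows can be read as undefined. That stands as a limit on the post-dose claim. It does not rescue the rule, because the SAP would then not say where these readings go.

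*The protocol sets no End of Treatment day for early stoppers.* This also stands. A reader might infer that the protocol fixes it at last dose + 7, but only the visit heading suggests so. The End of Study result does not depend on it.

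*Day 33 is a calendar label, and a Day 36 reading lies correctly within it.* That is defensible for an efficacy model in study time. It is not for a safety row that the protocol and SAP 2.1 identify as the End of Treatment visit, 7 days after last dose.

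*Little of the safety reporting depends on these windows.* This is largely right. A reader might infer that the rule hides acute post-dose falls or persisting abnormalities. The documents do not support that. A fall recorded at a dosed visit stays in that visit's row. AEs and adjudicated DLTs are reported separately, and any FEV1 fall of 15% or more is counted, plotted and listed (SAP 4.10.1.4). Laboratory shift tables use all post-baseline values, and out-of-range counts are also given overall (4.10.2.1). ECG has a single post-baseline window. In addition, the addendum repeats the efficacy analyses in subjects with at least 10 doses, which excludes every stop after doses 1 to 6. The SAP's main exploratory models still include them.

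**Conclusion.** The point holds in a bounded form. The End of Study misplacement follows directly from Table 5 and protocol 7.4.12 on the Monday-Wednesday-Friday schedule. It affects stops after doses 1 to 6 for laboratory and 2 to 6 for spirometry and vital signs, and no later stops. The post-dose misplacement is conditional on 00:00 standing in for the dose time; if it does not, those windows are undefined for undosed visits. Its counts also assume End of Treatment at last dose + 7 days, though some misplacement remains at +3, +5 and +9.

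What is distorted is the by-time-point safety summaries, including change from baseline to end of treatment, and the exploratory mixed and dose-response models that use the same windows. The documents do not give the number of early stoppers, so the effect on results cannot be sized beyond 1/6 of a planned active group per subject. Nor can it be said that some dose groups would be affected more than others. The change should be made, but the primary endpoints of AEs and DLTs do not depend on it.

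**What to change.** Amend SAP 4.2.7.1 and Table 5 for MAD subjects with fewer than 12 doses:

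- (a) In by-time-point safety tables, assign the End of Treatment and End of Study visits of early stoppers to rows labelled End of Treatment (7 days after last dose) and End of Study (28 days after last dose), using the actual last dose date instead of the notional Day 26. Naming the rows this way avoids putting, say, a Day 15 reading under a Day 33 label.
- (b) Fill any post-dose row only from visits where a dose was actually given, and report undosed visits as off-treatment.

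Calendar-day windows may stay for the exploratory efficacy models, if the SAP says so. The cost is SAP wording and window programming from dose dates already collected; no new data are needed. The small downside is fewer subjects in some post-dose cells.
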